# 7. Rationale and background

The active ingredient of InductOs is dibotermin alfa or recombinant human Bone Morphogenetic Protein 2. Its osteoinductive properties result in the induction of new bone tissue at the site of implantation.

InductOs is approved for:

- single-level lumbar interbody spine fusion as a substitute for autogenous bone graft in adults with degenerative disc disease who have had at least 6 months of non-operative treatment for this condition.
- treatment of acute tibia fractures in adults, as an adjunct to standard care using open fracture reduction and intramedullary unreamed nail fixation.

Instructions for proper preparation and administration of dibotermin alfa/ACS are provided in the Summary of Product Characteristics (SmPC) and instructions for reconstitution are provided in the labelling of the pack. The aforementioned instructions consist of routine measures to minimise important identified (heterotopic ossification, osteolysis/resorption bone increased, fluid collection) and potential risks (medication errors and incorrect use, malignancies, antibody formation) by providing information on the measures to take during administration of dibotermin alfa/ACS or situations to avoid.

Additional risk minimisation measures (aRMM) to increase awareness about the identified risk of heterotopic ossification (especially in posterior surgical approaches for lumbar interbody fusion) and the potential risk of medication errors and misuse are available in the form of educational materials. These educational materials also aim at providing guidance on how to manage these risks. The aRMM present the information from the Summary of

Product Characteristics (SmPC) supported with visual aids, e.g. a demonstration of the correct preparation technique. The aRMM and related educational materials contain no information which is not contained in the SmPC.

InductOs educational materials consist of a preparation guide, two videos (one for each indication), and the SmPC. The educational materials can be accessed through a dedicated website, or upon request to the MAH.

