## Secondary question:

• Was the knowledge on the risk of heterotopic ossification and minimization measures obtained from the SmPC, educational materials, professional training and literature, or a combination of these?

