## 9. Research methods

#### 9.1 Study design

This study is a cross-sectional cohort analysis of InductOs-using spine surgeons to establish:

• their current level of knowledge regarding heterotopic ossification,

 the current level of knowledge, and degree of access to or utilisation of educational materials about the potential for post-surgical heterotopic ossification and practical risk minimisation measures.

A cross-sectional cohort study methodology was judged to be appropriate to meet the expectations of the European Medicines Agency (EMA) based on:

- The nature of the medicinal product: single use implantation in a relatively small target population
- The nature of heterotopic ossification which is not an uncommon adverse event of many orthopaedic procedures and it does not always manifest clinically
- The lack of appropriate data fields captured in the national spine registries across Europe,
- The period over which the educational materials have been available (since summer 2017)

The cohort study will be composed of an anonymous, online survey (see Annex 3) with the aim of answering the study questions outlined in section 8.

The screening for eligibility and online interviews will be conducted in the surgeon's native language. All materials will be prepared using the English master questionnaire as the baseline (see Annex 3). Translations will undergo appropriate quality checks prior to sign off by the research team.

The researchers will secure responses from 55 individuals from the four selected countries split proportionally based on usage, see section 9.5.

A pilot project of 2 surgeons will test the survey for clarity and accuracy of response and translated materials in an iterative manner. If no changes are made, then the pilot recruits will be included in the main cohort.

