#### *Third category*

- Used sources for guidance on InductOs administration
- Use of educational materials

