## 9.7 Data analysis

The study population will include all physicians who are screened, are eligible for this study, and completed the questionnaire. All statistical summaries in this study will be descriptive. Frequencies and percentages, with 95 % confidence intervals (CIs) where appropriate, will be presented. Country specific data will be presented. Additional exploratory analyses and sensitivity analyses may be conducted to identify difference between groups of responders.

The primary analysis is aimed at evaluating the proportion of physicians that is aware of the risk of heterotopic ossification and measures described in the educational materials to minimize that risk. A respondent is considered to be aware if they answer 75 % of the questions with regards to heterotopic ossification and the applicable minimization measures correctly. In the questionnaire there are 12 (sub)questions raised on the occurrence of heterotopic ossification and the related risk minimization measures. Hence a surgeon needs to answer 9 of these correct to be considered aware. In Annex 3 the (sub)questions included in the scoring of awareness are marked. The aRMM will be considered effective if 80 % of the respondents are aware of the described risk of heterotopic ossification and the appropriate measures to minimize them. With the targeted 55 respondents, this means 44 or more need to be aware.

The secondary analysis is aimed at identifying the source of physician knowledge. Based on the received data it will be determined to what extent the educational materials are used and are considered an important source of information for the respondents.

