## Questionnaire on InductOs

How many years have you been using InductOs?

- $(1) \le 5$  years
- (2) 6-10 years
- $(3) \ge 10$  years
- (4) Prefer not to answer

When was the last time you implanted InductOs?

- (1) 0 <3 months ago
- (2) 3 <6 months ago
- (3) 6 <9 months ago
- (4) 9 < 12 months ago
- (5) 12 24 months ago
- (6) I don't remember

Approximately how many patients have you implanted with InductOs in the past 2 years?

- (1) < 5
- (2) 5 < 10
- (3) 10-<15
- (4) 15-<20
- (5) > 20
- (6) I don't know

Please indicate in percentages how much of your time is spent in the following approaches during your procedures with InductOs. Must sum to 100%.

- (1) Anterior Lumbar Interbody Fusion (ALIF)
- (2) Posterior Lumbar Interbody Fusion (PLIF)
- (3) Transforaminal Lumbar Interbody Fusion (TLIF)
- (4) Oblique Lateral Interbody Fusion (OLIF) / eXtreme Lateral Interbody Fusion (XLIF)
- (5) Posterolateral Fusion (PLF)
- (6) Others (textbox)

When using InductOs in lumbar interbody spine fusion, how much rhBMP-2 do you usually implant in one intervertebral space?

- 1- Less than 4 mg
- 2- Between 4 mg and 8 mg
- 3- Between 8 mg and 12 mg
- 4- More than 12 mg

What best describes your use of the following tools, provided to physicians, when considering the use of InductOs or administering InductOs to a patient?

Tool	Never use	Sometimes use	Frequently use	Always use
Summary of				
Product				
characteristics /				
Package insert				
Educational				
materials				
Other				
information				
provided by the				
Market				
Authorisation				
Holder				
Information				
from peers				
Scientific				
publications				

Would you consider that the available information on the use and administration of InductOs is easy to access?

Y/N

(Note: for the questions below the following legend applies:

- Green text indicates a correct answer
- Orange text indicates a (sub)question which is considered for assessing awareness)

Which of the following are common adverse reactions you associate with InductOs when administering InductOs during lumbar interbody fusion?

1		37 / NT
1-	Urinary retention	Y / N
2-	Fluid collection, like localised edema or (pseudo)cyst	Y/N
3-	Malignancies	Y/N
4-	Neuralgia	Y / N
5-	Osteolysis / increased bone resorption	Y/N
6-	Pseudarthorsis	Y / N
7-	Radiculopathic complaints (radiculitis, radicular pain, radiating	Y / N
	pain, sciatica)	
8-	Heterotopic / ectopic ossification / additional bone growth	Y/N
9-	Back pain	Y / N
10-	Infections	Y / N

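### Annex 3 measures use of the educational materials but not access to them or knowledge that they exist, so non-use cannot be explained

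*Protocol*

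**What the plan says.** Section 9.1 lists, among the things the survey is to establish, "the current level of knowledge, and degree of access to or utilisation of educational materials about the potential for post-surgical heterotopic ossification". Sections 4.6 and 9.3 describe a second category of variables that covers awareness of the heterotopic ossification risk, of the educational materials, and of safe use.

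Annex 3 has two places where the materials could be addressed:

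- A use grid, introduced by "What best describes your use of the following tools, provided to physicians, when considering the use of InductOs or administering InductOs to a patient". It has five rows: SmPC or package insert, educational materials, other information from the marketing authorisation holder, peers, and publications. The scale runs from never to always.
- Directly after it, one yes/no item: "Would you consider that the available information on the use and administration of InductOs is easy to access".

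Section 7 defines the materials: "InductOs educational materials consist of a preparation guide, two videos (one for each indication), and the SmPC". It adds that they are reached through a website or by asking the marketing authorisation holder, and that their content does not go beyond the SmPC.

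The planned analysis is narrower than section 9.1. The third variable category in section 9.3 lists "Use of educational materials", and section 9.7 says that "it will be determined to what extent the educational materials are used and are considered an important source of information for the respondents".

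**The concern.** The access item asks about InductOs information of every kind. Coming straight after a grid that names five sources, a 'Yes' may refer to the package insert, colleagues or the literature as easily as to the materials. No other item asks whether the surgeon has heard of, received or opened the preparation guide, the lumbar video or the website.

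This matters for interpretation. Section 4.2 presents the study as measuring the effectiveness of the educational materials, and section 7 says the evaluation rests on process indicators because outcome indicators were not feasible. The materials have to be sought out on a website or requested, so reach cannot be taken for granted. If many respondents report no use, the report could not say whether they did not know of the materials, did not reach them, or knew them and preferred other sources. These explanations call for different responses from the sponsor.

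**Working it through.** The check compares what the protocol says will be measured with the items in Annex 3. No figure in the plan bears on the point; the sample-size calculation does not enter.

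**1. Inventory of Annex 3.** There are 3 demographic items, 5 on experience and practice with InductOs, the use grid, the access item, and 6 knowledge blocks (adverse reactions, statements on heterotopic ossification, filling the device, matrix placement, physical barrier, irrigation and drains): 3 + 5 + 1 + 1 + 6 = 16 blocks.

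**2. Stated target against item.**

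| Stated in the protocol | Item in Annex 3 | Specific to the materials? |
|---|---|---|
| Utilisation of the materials (9.1, 9.3, 9.7) | Grid row 'Educational materials' | Yes, subject to step 4 |
| Access to the materials (9.1) | Yes/no on ease of access to information | No, not named |
| Awareness of the materials (4.6, 9.3) | None | – |

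The bulleted list for the second category in section 9.3 does not carry the last variable forward, so the section's introduction and its own list already differ.

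**3. What the grid says about access.** Anyone answering 'Sometimes', 'Frequently' or 'Always' must have had access. Let N be the number answering 'Never use' among the planned 55.

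- Lower limit for the access proportion: (55 − N)/55, if no 'Never use' respondent had access.
- Upper limit: 55/55 = 1, if all of them had access but did not use the materials.
- Width of the range: N/55, that is 1/55 = 1.8 percentage points for each 'Never use' answer.

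The range closes only if N = 0. The yes/no item cannot narrow it, because it refers to information in general.

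**4. Overlap of two grid rows.** Under section 7 the SmPC is one of the educational materials; in the grid it has its own row. A surgeon who reads only the package insert could, on the protocol's definition, tick both rows. The lower limit in step 3 then holds only for a set that includes the SmPC and gives no firm limit for contact with the guide, video or website. The same overlap blurs the section 8 question on where knowledge came from, "Was the knowledge on the risk of heterotopic ossification and minimization measures obtained from the SmPC, educational materials, professional training and literature", which treats the SmPC and the materials as separate sources.

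**The case against.** The strongest reply is that section 9.1 says access *or* utilisation. Read as alternatives, the aim is served by the grid, which has a row for the materials on a four-level scale. Access appears in neither the primary nor the secondary research question, nor in the variable list or analysis of sections 9.3 and 9.7. The 80 % criterion does not depend on it. This stands, and it limits the point. A reader might infer that a stated aim goes wholly unanswered or that nothing about access can be reported. The documents do not support that: utilisation is measured, and any reported use gives a lower limit on access.

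A reader might also infer that the survey cannot identify surgeons who were reached without effect. That too goes further than the text allows. Users with a low awareness score can be found by crossing the grid row with the score, and section 9.7 permits exploratory comparisons between groups of respondents. The ambiguity lies in the 'Never use' answers.

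On the overlap, it is fair to say that Annex 3 as shown does not give respondents the section 7 definition, that the package insert has its own named row just above, and that a pilot of 2 surgeons tests clarity. Double ticking is therefore possible rather than shown. Even so, the protocol's definition and the questionnaire's labels do not agree, and the report will have to interpret the row under one or the other.

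Finally, better items would not tie awareness to the materials. Their content is all in the SmPC, and the design is a single cross-sectional sample without a comparator. That limit belongs to the design and would remain after the fix.

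**Conclusion.** The point holds in limited form. Annex 3 measures use of the educational materials but does not separately measure access to them or knowledge that they exist. The section 9.1 aim is met for utilisation and not for access, and the awareness-of-materials variable in sections 4.6 and 9.3 has no item. One access item exists and none is specific to the materials; one grid row is specific to them, with an unclear boundary against the SmPC row. The access proportion is known only to within N/55, where N is the number of 'Never use' answers.

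The effect is on interpretation of the secondary results. The awareness score, the 80 % criterion and the sample size are untouched, and it would be wrong to read this as a flaw in the primary conclusion.

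The conclusion assumes that Annex 3 as shown contains every survey item and that the telephone screening, whose questions are not reproduced, asks only about eligibility, as section 9.2 states.

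**What to change.** Before the survey is fielded:

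1. Reword the access item to name the preparation guide, the lumbar video and the website, each with three options: not aware, aware but not accessed, accessed. Ask about ease of access only of those who accessed them.
2. Relabel the grid row as educational materials other than the SmPC.
3. Add one descriptive table of the awareness result by access, with no causal claim.

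This splits 'Never use' into its components and supplies the missing awareness-of-materials variable. The cost is a slightly longer survey, translation of the changed text and one extra table; scoring and study size do not change.

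If the item is left as it is, limit the section 9.1 wording to utilisation, and drop awareness of the materials from the variables described in sections 4.6 and 9.3.

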11-	Retrograde ejaculation	Y / N
12-	Others, please specify	Y / N

As the terms ectopic and heterotopic ossification are used interchangeably in some publications, we will use heterotopic ossification to describe both concepts. Heterotopic

ossification is one of the known adverse reactions to InductOs. Can you please indicate for each of the following statements whether it is true or false?

1	Heterotopic ossification can occur during lumbar arthrodesis	True / False
2	Heterotopic ossification occurs with and without the use of InductOs	True / False
3	Heterotopic ossification forms quickly	True / False
4	Heterotopic ossification can lead to nerve compression	True / False
5	Radicular pain is never the result of heterotopic ossification	True / False
6	Heterotopic ossification can occur asymptomatic	True / False
7	Heterotopic ossification occurs more often in patients undergoing a surgery with an anterior approach than in surgery with a posterior approach.	True / False

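### The one heterotopic ossification item asked before the questionnaire discloses the risk carries a gloss that overlaps with the product's intended action, so an answer to it does not cleanly show awareness

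*Protocol*

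**What the plan says.** Annex 3 (Questionnaire on InductOs) asks "Which of the following are common adverse reactions you associate with InductOs when administering InductOs during lumbar interbody fusion" and lists options, each with Y/N. Option 8 is "Heterotopic / ectopic ossification / additional bone growth".

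The next question fixes the terminology: "As the terms ectopic and heterotopic ossification are used interchangeably in some publications, we will use heterotopic ossification to describe both concepts". It then tells the respondent that heterotopic "ossification is one of the known adverse reactions to InductOs", and puts seven true/false statements about it.

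Section 7 says of the active ingredient: "Its osteoinductive properties result in the induction of new bone tissue at the site of implantation".

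Section 9.7 sets the scoring: "In the questionnaire there are 12 (sub)questions raised on the occurrence of heterotopic ossification and the related risk minimization measures". It continues: "Hence a surgeon needs to answer 9 of these correct to be considered aware". The measures are judged effective if 80 % of respondents are aware, which is 44 of the targeted 55. The scored items are identified by colour in Annex 3: "Orange text indicates a (sub)question which is considered for assessing awareness". The colours do not survive in the text available for this review, which is no fault of the plan.

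**The concern.** Option 8 joins three labels under one answer. The first two are the concept that the questionnaire goes on to define. The third, *additional bone growth*, is outside that definition and does not say that the bone is in the wrong place. Location is what separates the risk from the intended effect. A surgeon who knows only that the product makes bone could accept the phrase and answer Y. The plain wording also helps a surgeon who does not recognise the technical term.

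The position of the item adds weight. The first primary question (section 8) is whether physicians understand the potential for heterotopic ossification. Every later item on the subject follows the sentence that names it as a known adverse reaction. No later item can therefore show whether the surgeon made the link to the product before being told. What is at stake is the item's own percentage and, if it is scored, one of the 12 marks behind the awareness proportion.

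**Working it through.** **1. The plan's own thresholds.** 0.75 × 12 = 9 correct answers, and 0.80 × 55 = 44 aware respondents. Both agree with section 9.7.

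**2. Is option 8 scored?** Counting each question in Annex 3 once: 1 (option 8) + 7 (true/false statements) + 1 (pre-implantation) + 2 (implantation) + 1 (post-implantation) = 12, the number in section 9.7. Without option 8 the count is 11. This supports scoring but does not prove it, because scoring only some sub-options could also give 12.

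**3. The wording side by side.**
- Defined concept: heterotopic and ectopic ossification, two terms treated as one.
- Intended action (section 7): new bone at the implantation site.
- Third label in option 8: bone growth with no stated site. It fits the intended action as well as it fits the risk.

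**4. Whose classification can change.** If option 8 is one of 12 items, a surgeon needs 9 in total. With 9 or more of the other 11 right, the surgeon is aware whatever the answer to option 8. With 7 or fewer, the surgeon is not aware in either case. Only a surgeon with exactly 8 of the other 11 is moved by it.

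**5. How often that happens.** Assume that the other 11 items are independent with a common probability p of a right answer. The protocol gives no p.

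P(exactly 8 of 11) = 165 × p^8 × (1 − p)^3

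| p | P(exactly 8 of 11) |
|---|---|
| 0.50 (guessing) | 0.081 |
| 0.70 | 0.257 |
| 0.75 | 0.258 |
| 0.80 | 0.221 |

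**6. Effect on measured awareness.** Let s be the share of all surgeons who answer Y only because of the gloss. The documents give no value; s = 10 to 30 % is assumed. The rise is s × P(exactly 8 of 11).

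- Guessing, p = 0.5: 0.10 × 0.081 = 0.8 points; 0.30 × 0.081 = 2.4 points.
- p = 0.70 to 0.80: lowest 0.10 × 0.221 = 2.2 points; highest 0.30 × 0.258 = 7.7 points.

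The overall range is about 1 to 8 points. If instead a share s answers N only because of the gloss, the same product gives a fall.

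**7. What that does to the 44-of-55 rule.** P(at least 44 of 55), binomial, starting from an assumed true awareness of 75 %:

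| Measured awareness | P(at least 44 of 55) |
|---|---|
| 75 % (no bias) | 0.25 |
| 75.8 % (+0.8) | 0.29 |
| 77.4 % (+2.4) | 0.39 |
| 79 % (+4) | 0.51 |
| 80 % (+5) | 0.58 |

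At the 90 % awareness expected in section 9.5 the same probability is 0.99, so there the verdict hardly depends on this item.

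**The case against.** The strongest answer is the question stem. It asks for adverse reactions, and the phrase comes third in one entry, after two technical terms, in a list of harms. A surgeon who takes it to mean wanted fusion has no reason to call it an adverse reaction and might answer N. This stands, and it defeats the inference that the error always runs towards finding the measures effective. Surgeons who recognise the technical term are probably less easily misled than those who do not, which makes a net upward bias plausible. Nothing in the protocol establishes it.

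A reader might also infer that this is the survey's one unprompted test of the risk. It is not. It is a closed Y/N item that names the reaction, so it tests aided recognition and can be guessed. What can be said is that it is the only such item asked before disclosure.

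A reader might take it as settled that a Y earns an awareness mark. That rests on the count to 12.

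The larger effects also need caution. The surgeon of concern does not know the reaction, yet p = 0.70 to 0.80 credits that surgeon with good answers elsewhere, and on the count above seven of the other 11 items are about heterotopic ossification. Independence is therefore doubtful, and the guessing figures may be nearer the truth for such surgeons. The 75 % starting point lies just below the threshold, where any small shift looks large.

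Finally, section 9.1 plans an iterative pilot for clarity and translation. That is the right stage for a wording repair, but a pilot of 2 surgeons cannot be relied on to reveal the ambiguity.

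**Conclusion.** The point holds as a minor one about the wording of a single item. Option 8 mixes the adverse reaction with language that fits the intended effect, in the only heterotopic ossification item placed before disclosure, so neither a Y nor an N cleanly shows what the surgeon knows. That conclusion needs no numerical assumption.

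The size does. If the item is scored, it is one mark in 12. With an assumed 10 to 30 % of surgeons answering Y only because of the gloss, measured awareness rises by about 1 to 2 points if they guess the other items and by up to about 8 points if they answer them with probability 0.70 to 0.80. Both the share and the independence of items are assumptions. The documents do not support a claim that the bias is one-way, or that this item alone would decide the study's verdict. If the item is not scored, only its own percentage is affected.

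**What to change.** Before launch, in the English master and every translation, replace *additional bone growth* in option 8 with a gloss that names the location, such as '(bone forming outside the intended fusion area)'. Alternatively, delete the phrase so that only the two terms defined in the next question remain.

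The cost is one wording change carried through the translations. If the phrase is deleted, a few surgeons who know the phenomenon only by a lay name may answer N; the location-specific gloss avoids that. Sample size, scoring rule and analysis stay as they are. Once the data are collected, the ambiguity cannot be removed from the answers.

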#### 9.10 Limitations of the research methods

Potential limitations to using this online survey include:

- Non-response bias: This is an inherent limitation in the survey study design. The non-response rate is reduced through the use of a telephone screening, short survey and the potential for compensation for time.
- Social desirability response bias: Surgeons may respond positively rather than truthfully. In order to reduce the probability of this type of bias, surveys are anonymous, questions are not leading, and are designed to elicit truthful responses.
- Sample is not random: A random sample of individuals meeting the selection criteria equalises the potential for bias to occur, making the sample potentially useful for generalising to the overall population. However, the small number of potential surgeons who would meet the selection criteria effectively removes the potential for randomisation.
- Self-selection bias: Even with the selection criteria it may be only the most motivated, experienced or engaged surgeons who participate leading to artificially high rates of awareness. This is reduced by decreasing the non-response bias, see above. Furthermore, the sample is chosen from all current users in the countries, regardless of quantity of InductOs provided in the past years.

These limitations are acknowledged and, given the nature of the data collected, should not greatly impact the conclusions drawn from the data collected from respondents. Efforts, where possible, will be made to address and reduce the impact of these limitations, see bullets above.

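### The preamble to the true/false block in Annex 3 discloses that heterotopic ossification is a known InductOs reaction, which cues one to three items and can bias the awareness score upward

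*Protocol*

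**What the plan says.** Annex 3 (Questionnaire on InductOs) takes the topic in this order:

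- A yes/no list asks "Which of the following are common adverse reactions you associate with InductOs when administering InductOs during lumbar interbody fusion". Option 8 is "Heterotopic / ectopic ossification / additional bone growth".
- The next block opens with a note on terminology and then says that heterotopic "ossification is one of the known adverse reactions to InductOs".
- Seven true/false statements follow. Statement 1 is "Heterotopic ossification can occur during lumbar arthrodesis" and statement 2 is "Heterotopic ossification occurs with and without the use of InductOs".

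On scoring, section 9.7 says: "In the questionnaire there are 12 (sub)questions raised on the occurrence of heterotopic ossification and the related risk minimization measures". Nine correct answers make a surgeon aware, and 44 aware out of 55 make the measures effective. Annex 3 marks the scored items and the correct answers by colour.

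Section 9.10, under social desirability bias, gives as mitigation that "surveys are anonymous, questions are not leading, and are designed to elicit truthful responses".

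**The concern.** The first primary question in section 8 is whether surgeons understand that heterotopic ossification can follow interbody fusion. Partway through the test, the questionnaire tells them that the product is known to cause it. A surgeon who did not know this can then answer some items from the questionnaire itself.

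The score feeds a fixed threshold per respondent and a second one for the study, so a few points gained on cued items could move surgeons into the aware group and help the measures to be called effective. Section 9.10 already concedes that self-selection may raise awareness artificially. This cue would act in the same direction and, unlike self-selection, is easy to avoid.

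**Working it through.** **The plan's thresholds.** 0.75 × 12 = 9 and 0.80 × 55 = 44. Both agree with section 9.7.

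**Which items the sentence helps with.**
- Option 8 comes before the sentence. It is exposed only if both are on one page or earlier answers can be changed. Section 9.2 describes a personal emailed link and section 9.6 a login and the survey software; neither says whether answers lock.
- Statement 1 is largely answered.
- Statement 2 is half answered: the sentence covers use with InductOs and is silent on use without it.
- Statements 3 to 7 are not answered. For example, statement 7 is "Heterotopic ossification occurs more often in patients undergoing a surgery with an anterior approach than in surgery with a posterior approach". Nor are the filling, placement, barrier, irrigation and drain questions.

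**Whether cued items are scored.** The colour marking cannot be read in the text available for this review. Section 9.7 says the 12 cover occurrence as well as minimisation measures, and the implantation questions cover technique only. So some scored items must come from the adverse-reaction list or the true/false block. One count gives exactly 12: option 8 (1) + statements (7) + technique questions (4). Other counts are possible.

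**Size, as a sensitivity range.** Item difficulty is not in the documents, so the per-item probability p is assumed. I take yes as the keyed answer to option 8 and true for statements 1 and 2, and treat items and respondents as independent. With k items given away:

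P(aware) = P[Bin(12 − k, p) ≥ 9 − k]

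P(effective) = P[Bin(55, P(aware)) ≥ 44]

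For p = 0.75 and k = 0: 0.258 + 0.232 + 0.127 + 0.032 = 0.649.

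| p | P(aware), k = 0 / 1 / 2 | P(effective), k = 0 / 1 / 2 |
|---|---|---|
| 0.60 | 0.225 / 0.296 / 0.382 | 0.00 / 0.00 / 0.00 |
| 0.70 | 0.493 / 0.570 / 0.650 | 0.00 / 0.00 / 0.01 |
| 0.75 | 0.649 / 0.713 / 0.776 | 0.01 / 0.10 / 0.41 |
| 0.80 | 0.795 / 0.839 / 0.879 | 0.54 / 0.83 / 0.97 |
| 0.85 | 0.908 / 0.931 / 0.950 | 0.996 / 1.00 / 1.00 |
| 0.90 | 0.974 / 0.981 / 0.987 | 1.00 / 1.00 / 1.00 |

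With three items given away at p = 0.75, P(aware) is 0.834.

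**Unequal difficulty.** With ten items at 0.80, suppose the two cued items would be right 95% of the time without help. Giving them away moves P(aware) from 0.859 to 0.879, about 2 points. If they would be right half the time, it moves from 0.653 to 0.879, about 23 points. If they are not scored, nothing changes.

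**The case against.** The only item that asks directly for the link between product and reaction, option 8, is put before the disclosure. Page layout and back-navigation are survey-programming settings that a protocol commonly omits, so silence on them is not an error. The cue on the statements is partial: the sentence does not mention arthrodesis, the product also has a tibial indication, and nothing is said about occurrence without the product. Seven statements on one reaction in a survey about one product signal the link anyway. The model sets cued items to 100% correct, which is generous for a half-cued item. Section 9.5 expects 90% aware, which under this model is about 85% per item; there P(effective) is at least 0.996 with or without the cue.

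Most of this stands, and it limits the size. It rules out three stronger inferences that a reader might draw:

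- *That awareness is inflated.* Neither the scored items nor their difficulty can be established from the text available.
- *That the cue carries the result over 80% aware.* At 75% per item this needs three items fully given away (0.834); two leave it at 0.776.
- *That the section 9.10 statement is untrue.* It covers the whole survey and addresses social desirability. One sentence bearing on a few items makes it inexact for those items only.

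The objection does not remove the direction of the bias, nor the fact that analysis cannot undo it after data collection.

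**Conclusion.** The concern holds in a limited form. The sentence cues statement 1 and half of statement 2, and option 8 if that answer is visible alongside it or can be revisited. If those items are scored, any bias in the proportion aware is upward.

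With one or two items given away and equal item difficulty between 0.60 and 0.90, P(aware) rises by about 1 to 16 points. Unequal difficulty widens this to the 23 points shown above, and the effect is zero if the items are unscored. The study verdict is sensitive mainly when true performance is around 75% to 80% per item, and hardly at all near the protocol's own expectation. All of this rests on assumed item probabilities and independence. The sponsor's colour copy of Annex 3 would settle which items count.

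**What to change.** Before fielding:

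1. Delete the sentence that names heterotopic ossification as a known reaction to the product. Keep the terminology sentence before it; the true/false items work without the rest.
2. Show the adverse-reaction list on its own page and lock the answers once submitted.
3. If the sentence is kept, qualify the section 9.10 statement on leading questions for the items it cues.

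The cost is one deleted sentence, to be carried into each translation, and one setting in the survey tool. The drawback is that respondents cannot correct a mis-click on the locked page.
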